#### **5.13.1.1. Deaths**

A listing of all deaths will be provided. Listing will include patient identification including the treatment, site number, date of death, age at the time of enrollment, sex, MedDRA PT of associate AE, time from first dose of study drug to death, time from last dose of study drug to death (if patient had discontinued study drug), cause of death as reported by investigator, caused of death as adjudicated by clinical endpoint committee (CEC).

#### **5.13.1.2. Other Serious Adverse Events**

The number and percentage of patients who experienced a SAE (including deaths and SAEs temporally associated or preceding deaths) during the study follow-up will be summarized by treatment using MedDRA PT nested within SOC. Events will be ordered by decreasing frequency within SOC.

A listing of all SAE will be provided. Listing will include treatment, patient identification including the site number, date of event, age at the time of enrollment, sex, MedDRA SOC and PT, severity, outcome, relationship to study drug, time from first dose of study drug to the event, time from most recent dose to event (if patient has discontinued study drug prior to the event).

#### **5.13.1.3. Discontinuation from Study Due to Adverse Event**

The number and percentage of patients who prematurely discontinue study due to AE will be summarized by treatment using MedDRA PT nested within SOC. Events will be ordered by decreasing frequency within SOC.

#### **5.13.1.4. Discontinuation from Study Drug Due to Adverse Event**

The number and percentage of patients who prematurely discontinue study drug due to AE will be summarized by treatment using MedDRA PT nested within SOC. Events will be ordered by decreasing frequency within SOC. Time-to-event analysis of time to study drug discontinuation by treatment as well as time to study drug discontinuation due to AE will be conducted.

### 5.13.2. Special Safety Topics

#### 5.13.2.1. Hypoglycemic Events

Definitions of different categories of hypoglycemic events are as follows:

	Symptoms and/or Signs of hypoglycemia	Blood Glucose Level
Glucose Alert Value:		
Documented symptomatic hypoglycemia	Yes	$\leq 70$ mg/dL (3.9 mmol/L)
Documented asymptomatic hypoglycemia	No	$\leq 70$ mg/dL (3.9 mmol/L)
Documented unspecified hypoglycemia	Unknown	$\leq 70$ mg/dL (3.9 mmol/L)
Clinically Significant Hypoglycemia:		
Clinically significant Documented symptomatic hypoglycemia	Yes	$< 54$ mg/dL (3.0 mmol/L)
Clinically significant Documented asymptomatic hypoglycemia	No	$< 54$ mg/dL (3.0 mmol/L)
Clinically significant Documented unspecified hypoglycemia	Unknown	$< 54$ mg/dL (3.0 mmol/L)
Severe Hypoglycemia		

**Severe hypoglycemia:** Defined as an episode with severe cognitive impairment requiring the assistance of another person to actively administer carbohydrate, glucagon, or other resuscitative actions. Severe hypoglycemia will be reported as a SAE. Severe hypoglycemia will be considered an adverse event of special interest (AESI).

**Nocturnal hypoglycemia:** Defined as any hypoglycemic event that occurs between bedtime and waking.

To avoid duplicate reporting, all consecutive hypoglycemic events in the same category, occurring within a 1-hour period may be considered to be a single hypoglycemic event.

Statistical summaries and analyses will exclude hypoglycemia events occurring after initiation of a new antihyperglycemic therapy. Severe hypoglycemia and hypoglycemia incidence (with blood glucose level  $\leq 70$  mg/dL [3.9 mmol/L] or  $< 54$  mg/dL [3.0 mmol/L], separately) as well as rate per patient year of exposure will be provided by treatment. The incidence of hypoglycemic event will be analyzed using logistic regression with treatment, country/pooled country, SGLT2i use at baseline (Yes/No) and baseline HbA1c ( $\leq 8.5\%$ ,  $> 8.5\%$  [ $\leq 69$ ,  $> 69$  mmol/mol]) as the fixed effects. The rate of hypoglycemic episodes per patient year will be analyzed using a generalized

linear mixed-effects model assuming the number of hypoglycemic episodes follow a negative binomial distribution with mean modeled using country/pooled country, SGLT2i use at baseline (Yes/No), baseline HbA1c ( $\leq 8.5\%$ ,  $> 8.5\%$  [ $\leq 69$ ,  $> 69$  mmol/mol]) and treatment as fixed effects. The logarithm of days during analysis interval will be adjusted as an offset to account for possible unequal treatment duration of follow up between patients.

Summary of hypoglycemic events will also be provided in subjects on or not on stable dose of sulfonylureas, separately.

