Unless specified otherwise, safety assessments will be based on all available data, irrespective of whether they were obtained after the participants had discontinued the study drug or whether the participant had been given rescue medication. Summary statistics will be provided for incidence of TEAEs, serious adverse events, and study discontinuation due to AEs or death during the treatment period. Counts and proportions of subjects experiencing AEs will be reported for each treatment group, and Fisher’s exact test will be used to compare the treatment groups. For continuous laboratory analytes, summary statistics will be provided by visit, with statistical comparisons among treatment at each visit conducted using an MMRM analysis. Selected safety analysis (for example, hypoglycemia) will be conducted after excluding data while on rescue therapy. Additional details, including analysis of AEs of special interest, will be provided in the SAP.

2. Schedule of Activities

The Schedule of Activities described below should be followed for all patients enrolled in Study GPGM. However, for those patients whose participation in this study is affected by severe acute respiratory syndrome coronavirus 2 (SARS-CoV-2), the virus that causes the novel Coronavirus Disease 2019 (COVID-19), please refer to [Appendix 8](#) for additional instructions.

Table GPGM.1. Schedule of Activities

	Study Period I		Study Period II 52 Weeks																								Study Period III Variable				Study Period IV				
	Screening Lead in		Treatment Period																								Safety F/U								
Visit	1	2	3 ^a	4	5	6	7	8	9	10	11	12	13	14	15	16	17	18	19	20	21	22	23	24	25	26	27	28	29	FT V ^z	ET ^b	801			
Week of Treatment	-3	-2	0	1	2	3	4	5	6	7	8	10	12	15	16	20	23	24	28	32	35	36	42	52	62	72	78	88	104			4 week post end of tx			
Allowable Deviation (days) ^c	-	±3	±7	±3	±3	±3	±3	±3	±3	±3	±3	±3	±3	±3	±3	±3	-	±3	±3	±3	-	±3	±7	±7	±7	±7	±7	±7	±7			±3			
Fasting Visit ^d			X		X		X				X		X		X	X		X					X	X			X		X	X	X	X			
PK only Visit																	X				X														
Telephone Visit						X		X	X			X																							
Informed consent	X																																		
Randomization			X																																
Clinical Assessments																																			
Medical history ^e	X																																		
Physical	X																								X							X			
Height	X																							X											
Weight ^f	X		X				X				X		X		X	X		X				X	X	X	X	X	X	X	X	X	X	X	X	X	

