10.3.4. Safety Analyses

Unless specified otherwise, safety assessments will be guided by an estimand comparing safety of LY3298176 doses with insulin glargine irrespective of adherence to study drug or initiation of rescue therapy. Thus, safety analysis will be conducted using Safety Analysis Set. Selected safety analysis will be conducted after excluding data on rescue therapy.

Adverse events will be coded from the actual term using the Medical Dictionary for Regulatory Activities (MedDRA) and reported with preferred terms and system organ class. Selected notable AEs of interest may be reported using high-level terms or Standardized MedDRA Queries. Summary statistics will be provided for incidence of TEAEs, serious adverse events (SAEs), study discontinuation due to AEs, study drug discontinuation due to AEs, deaths, and other CV endpoints. Counts and proportions of subjects experiencing AEs will be reported for each treatment group, and Fisher's exact test will be used to compare the treatment groups.

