10.3.4.1. Hypoglycemic Events

Incidence of documented symptomatic hypoglycemia events and severe hypoglycemia in each category (either total or nocturnal) will be compared between LY3298176 doses and insulin glargine using negative binomial regression analysis. Summaries and analysis will be repeated excluding data following initiation of rescue antihyperglycemic therapy.

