**Table GPGM.5.1. Analysis Populations/Data Sets**

Population/Data Set	Description
Screened population	All participants who sign informed consent
Randomized population	All patients who are randomly assigned a treatment arm
Modified intent-to-treat (mITT) population	All randomly assigned participants who are exposed to at least 1 dose of study drug.
Efficacy analysis set (EAS)	Data obtained during Study Period II and III from mITT, excluding patients discontinuing study drug due to inadvertent enrollment and data after initiating rescue antihyperglycemic medication or discontinuation of study drug (last dose date + 7 days).
Full analysis set (FAS)	Data obtained during Study Period II and III from mITT, excluding patients discontinuing study drug due to inadvertent enrollment, regardless of adherence to study drug or initiation of rescue antihyperglycemic medication.
Safety analysis set (SS)	Data obtained during Study Period II, III, and IV from mITT, regardless of adherence to study drug or initiation of new antihyperglycemic medication.

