#### **5.13.3. Renal Safety**

A subpopulation of “Patients with T2DM and renal dysfunction” is of study interest, will be identified as  $eGFR < 60 \text{ mL/min/1.73m}^2$  or  $UACR > 300 \text{ mg/g}$  at baseline. The following analyses will be done in this subpopulation:

Summary and change from baseline in  $eGFR$  will be analyzed in MMRM analysis using actual measurements. The same analysis will be done for  $UACR$  in log scale. The analysis will be conducted utilizing for changes from baseline through post-baseline with a MMRM using restricted maximum likelihood (REML). The model will include stratification factors (country/pooled country, baseline  $HbA1c$  ( $\leq 8.5\%$ ,  $> 8.5\%$  [ $\leq 69$ ,  $> 69 \text{ mmol/mol}$ ]), baseline SGLT2 inhibitor use (Yes or No)), treatment group, visit, and treatment-by-visit interaction as fixed effects, and baseline value of the corresponding renal marker (log scale if the corresponding renal parameter is analyzed on the log scale) as a covariate.

Shift table for  $eGFR$  and  $UACR$  will be done in the renal dysfunction subpopulation. Treatment-emergent adverse events in the renal dysfunction subpopulation will be summarized by treatment using MedDRA PT nested within SOC. Serious adverse events in the renal dysfunction subpopulation will be provided. Analyses of changes from minimum baseline value to minimum postbaseline value will be performed for  $eGFR$ . Analyses of changes from maximum baseline value to maximum postbaseline value will be performed for  $UACR$ , Calcitonin, ECG parameters and vitals (pulse, SBP and DBP). Severe hypoglycemia and level 2 hypoglycemia events will be summarized by treatment, excluding hypoglycemia events occurring after initiation of rescue therapy. Post-baseline threshold analysis will be done for  $eGFR$  ( $< 15$ ,  $< 30$ ,  $< 45$ , and  $< 60$ ) and “ $eGFR < 60$  or  $UACR > 300$ ”.

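### SAP 5.13.2.1 plans hypoglycemia analyses only with events after a new antihyperglycemic therapy removed; the protocol's all-data comparison is not carried forward

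*SAP*

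**What the plan says.** Protocol 10.3.4.1 takes documented symptomatic and severe hypoglycemia, total and nocturnal, which "will be compared between LY3298176 doses and insulin glargine using negative binomial regression analysis". It then adds: "Summaries and analysis will be repeated excluding data following initiation of rescue antihyperglycemic therapy". The first analysis carries no exclusion, so the default in Protocol 10.3.4 applies, namely safety assessed "irrespective of adherence to study drug or initiation of rescue therapy". The protocol synopsis adds: "Selected safety analysis (for example, hypoglycemia) will be conducted after excluding data while on rescue therapy".

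The SAP's safety analysis set in Table GPGM.5.1 is "Data obtained during Study Period II, III, and IV from mITT, regardless of adherence to study drug or initiation of new antihyperglycemic medication". SAP 5.13 says that some safety analyses may leave out data after new antihyperglycemic therapy. SAP 5.13.2.1 makes this the rule for hypoglycemia: "Statistical summaries and analyses will exclude hypoglycemia events occurring after initiation of a new antihyperglycemic therapy". A logistic model for incidence and a negative binomial model for rate follow under that rule. For the rate model, "The logarithm of days during analysis interval will be adjusted as an offset".

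For the renal dysfunction subpopulation, SAP 5.13.3 summarizes severe and level 2 events "excluding hypoglycemia events occurring after initiation of rescue therapy".

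**The concern.** The protocol plans a pair of analyses and the SAP keeps one of them. The missing one compares hypoglycemia between each dose and insulin glargine over all follow-up, whatever else the patient was given later. That matches the SAP's own default for safety.

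The remaining version stops counting a patient's events at a point that is decided after randomisation, in an open-label trial, under rules that differ by arm. If patients who start new therapy differ between arms in number or in proneness to hypoglycemia, the comparison is between selected periods of follow-up. Without the all-data version beside it, a reader cannot see whether the conclusion depends on the exclusion.

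Two wording points add to this. The SAP's trigger is new therapy, while the protocol and SAP 5.13.3 use rescue. The SAP also does not say that the exposure offset ends when event counting ends.

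**Working it through.** The plan gives no figure on this point to reproduce. The check is mainly a comparison of text.

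**1. Which analyses are planned**
- Protocol 10.3.4.1: all safety data, then a repeat without post-rescue data.
- SAP 5.13.2.1: the excluded version only, without qualification.
- Protocol 10.3.1 and SAP 5.2 allow non-principal changes if the justification appears in the SAP or the clinical study report. The SAP's revision history describes the update to 5.13.2.1 as adding clarity. It does not say that an analysis was removed.

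**2. What is still reported on all data**
- Severe hypoglycemia is reported as an SAE (SAP 5.13.2.1). SAP 5.13.1 compares treatment-emergent events by treatment at system organ class and preferred term level. SAP 5.13.1.2 summarizes and lists all SAEs. Neither section excludes events after new therapy.
- For documented hypoglycemia at either glucose threshold, the safety sections name no all-data incidence or rate comparison. Four composite responder endpoints in SAP 5.12.4 use hypoglycemia as one component, but they do not compare hypoglycemia itself.
- For severe hypoglycemia, the logistic and negative binomial models are under the exclusion.

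**3. The trigger**
- Protocol 5.1 and SAP 4.1 say that new therapy started for safety follow-up is not rescue. All patients are off study drug in that period and receive another glucose-lowering treatment.
- SAP 5.13.2.1 therefore drops follow-up events once such therapy starts, while SAP 5.13.3 keeps them. SAP 3.4 nevertheless lists occurrence of hypoglycemic events among the comparisons to be made at the end of safety follow-up.

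**4. Dependence on arm**
- Protocol 9.2.2.2 applies the rescue criteria to glargine patients only after Week 12, with further titration as the first measure.
- The same section allows basal insulin as rescue only in the LY3298176 arms.
- Protocol 7.3 confirms that the trial is open-label.

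**5. Illustrative size**

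The documents do not give the share *s* of patients who start new therapy. Protocol 10.1 assumes that no more than 28% are rescued or stop study drug by Week 52, as a sizing assumption for the efficacy estimand. Take *s* = 0.28 as an upper-end assumption, with starts uniform over Weeks 0 to 52 and all these patients staying in follow-up:
- Patients affected: 0.28 × 939 = 263 on glargine and 0.28 × 313 = 88 per LY3298176 arm.
- Person-time affected to Week 52: 0.28 × 26/52 = 0.14.
- Person-time affected to Week 104, with no starts after Week 52: 0.28 × (26 + 52)/104 = 0.21.
- With *s* = 0.02, the two person-time figures are 0.01 and 0.015.

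For the offset, assume a constant event rate. Counted events are then proportional to 1 − *s*/2 over 52 weeks. If the offset is cut at the same date, this factor cancels. If it is not cut, the LY3298176-to-glargine rate ratio is multiplied by (1 − *s*_LY/2)/(1 − *s*_G/2). The shares below are assumptions:
- 28% in both arms: 0.86/0.86 = 1.00.
- 10% glargine, 2% LY3298176: 0.99/0.95 = 1.04; reversed, 0.96.
- 28% glargine, 5% LY3298176: 0.975/0.86 = 1.13; reversed, 0.88.

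**The case against.** The best defence is that the exclusion is legitimate and foreseen. The SAP's safety default begins with an allowance for exceptions, SAP 5.13 permits this kind of cut, and the protocol synopsis names hypoglycemia as an example of it. There is also a rationale: insulin can be used as rescue, and later hypoglycemia may then not reflect the randomised drug. All of this stands as support for having an excluded version. It does not cancel the all-data analysis in Protocol 10.3.4.1, which the synopsis is consistent with, and it does not explain the change of trigger. A justification might still appear in the clinical study report, which is not available here.

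The defence is right to resist four stronger readings that a reader might infer:
- *Severe episodes after a switch disappear.* They do not. They remain in the all-data adverse event comparisons and in the SAE summaries and listings.
- *The SAP extends the trigger to therapy begun after stopping study drug.* Protocol 7.7 already describes rescue as possibly indicated after early discontinuation of study treatment. The clear addition is therapy started in safety follow-up, a period of about four weeks.
- *A key outcome is affected.* In this trial's tiers, hypoglycemia is an additional secondary safety outcome without type 1 error control.
- *The rate model is biased.* Days in the analysis interval may well mean the days over which events are counted. The wording is ambiguous, not shown to be wrong.

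**Conclusion.** The point holds as a protocol–SAP inconsistency with a cheap remedy. SAP 5.13.2.1 omits the all-data hypoglycemia comparison that Protocol 10.3.4.1 puts first. What is lost is all-data incidence and rate comparison of documented hypoglycemia at both thresholds, and all-data modelling of severe hypoglycemia. The trigger differs between sections, most clearly for safety follow-up, and the end of the offset is unstated.

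The documents do not show that any result would be biased, or in which direction. The 14% of person-time to Week 52 rests on treating a sizing ceiling as the rate of starting new therapy, and on uniform timing. The rate-ratio shifts also need unequal arms and an uncut offset; without both, and at a constant event rate, there is no shift. The case for the change rests on the mismatch in the text and on the arm-dependent, open-label trigger, not on these figures.

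**What to change.** In SAP 5.13.2.1:
- Run the incidence and rate models on the full safety analysis set, as Protocol 10.3.4.1 plans, and present the excluded version as the repeat.
- Choose one trigger term, define it (including how therapy started in safety follow-up is treated), and use it in 5.13.2.1 and 5.13.3.
- State that in the excluded version each patient's offset interval ends on the date from which events are no longer counted.

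The cost is one more run of models already specified and a few lines of SAP text. The downside is a second set of hypoglycemia tables.

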- x PK samples will not be collected from patients who were randomized to insulin glargine since it is an open-label study. PK samples will be collected at these visits at time windows of 1 to 24 hours, 24 to 96 hours, OR 120 to 168 hours post dose, as assigned by IWRS. Dependent on the time-windows to which a patient gets assigned, they may be required to come to site for PK-specific visits. Draw PK at ET visit only if patient discontinues study prior to Week 35. Visits 10 and 14 are for all patients, but only those patients assigned to PK will get a PK blood draw. Visits 17 and 21 are for patients assigned to a PK blood draw only.
- y PROs should be completed before any other study procedures if the patient is not adversely affected by the fasting condition or completed after the patient has sufficiently recovered from the preceding visit procedures.
- z When the sponsor determines that the study has met the completion criteria, all patients remaining in the study will return to the site for a FTV within approximately 30 days. The safety follow-up visit will be approximately 30 days after the FTV.

Note: Patients will be required to collect a daily BG and a weekly 4-point SMBG.

3. Introduction

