7.2.1.2. Insulin Glargine

Dosing for patients randomized to insulin glargine will start at 10 units once daily. Patients should administer their daily doses at the time of day agreed upon between the patient and the investigator, typically before bedtime. Patients assigned to the insulin glargine treatment arm will be instructed to adjust insulin glargine doses to a target FBG of <100 mg/dL (5.6 mmol/L) based on the median value of the last 3 self-monitored fasting blood glucose (SMBG) values according to the schedule below (Riddle et al. 2003). Insulin glargine dose adjustments should occur once in a week. After Week 8, patients will continue to adjust insulin glargine per the titration algorithm; the insulin glargine dose will be also reviewed and revised, as needed, at subsequent office visits. There will be no central oversight of insulin glargine titration. Add-on

glycemic rescue therapy should be initiated for patients who met prespecified criteria for severe, persistent hyperglycemia, and further titration of glargine cannot control the condition (see [Table GPGM.4](#)).

Table GPGM.4. Titration of Insulin Glargine

Median Fasting Blood Glucose ^a		Adjustment of Insulin Glargine
mg/dL	mmol/L	
≤70	≤3.9	Decrease by 2 to 4 units ^{b,c}
71 to 99	4.0 to 5.5	No adjustment
100 to 119	5.6 to 6.6	Increase by 2 units
120 to 139	6.7 to 7.7	Increase by 4 units
140 to 179	7.8 to 9.9	Increase by 6 units
≥180	≥10.0	Increase by 8 units

Abbreviation: SMBG = self-monitored blood glucose.

^a Based on the last 3 self-monitored fasting blood glucose (SMBG) values.

^b Dose should also be decreased by 2 to 4 units in the following situations:

- If multiple episodes of nonsevere hypoglycemia were recorded during the assessment period at any time during the day; and/or
- If at least 1 episode that met the criteria for severe hypoglycemia (events requiring assistance to administer therapy) or was associated with self-monitored blood glucose (SMBG) value <54 mg/dL (<3.0 mmol/L) was recorded during the assessment period.

^c If only 1 hypoglycemic episode with SMBG value ≥54 mg/dL (≥3.0 mmol/L) and ≤70 mg/dL (≤3.9 mmol/L) was recorded, insulin dose should not be changed.

Source: Riddle et al. 2003.

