- **Severe hypoglycemia** is defined as an episode with severe cognitive impairment requiring the assistance of another person to actively administer carbohydrate, glucagon, or other resuscitative actions. These episodes may be associated with sufficient neuroglycopenia to induce seizure or coma. Blood glucose measurements may not be available during such an event, but neurological recovery attributable to the restoration of BG to normal is considered sufficient evidence that the event was induced by a low BG concentration.

Nocturnal hypoglycemia:

- **Nocturnal hypoglycemia** is defined as any hypoglycemic event that occurs between bedtime and waking.

If a hypoglycemic event meets the criteria of severe, it should be recorded as serious on the AE eCRF and reported to Lilly as an SAE.

To avoid duplicate reporting, all consecutive BG values ≤ 70 mg/dL (3.9 mmol/L) occurring within a 1-hour period may be considered to be a single hypoglycemic event (Weinberg et al. 2010; Danne et al. 2013).

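### SAP 5.13.2.1 does not carry forward the protocol's symptomatic and nocturnal hypoglycemia comparisons and narrows the 1-hour merge rule, with no reason stated

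*SAP*

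**What the plan says.** Protocol 10.3.4.1 sets the comparison: "Incidence of documented symptomatic hypoglycemia events and severe hypoglycemia in each category (either total or nocturnal) will be compared" between the tirzepatide doses and insulin glargine, by negative binomial regression.

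SAP 5.13.2.1 opens with a table of six rows (symptomatic, asymptomatic and unspecified, each at ≤70 and at <54 mg/dL), followed by severe hypoglycemia. It also defines a nocturnal event: "Defined as any hypoglycemic event that occurs between bedtime and waking". The sentence naming the outcomes starts "Severe hypoglycemia and hypoglycemia incidence (with blood glucose level" and gives the two cut-offs, with matching rates per patient-year. Incidence goes to logistic regression and the episode rate to a negative binomial model. Neither symptoms nor time of day enters that sentence or the models.

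The counting rules also differ. Protocol 9.2.2.1 says "all consecutive BG values ≤ 70 mg/dL (3.9 mmol/L) occurring within a 1-hour period may be considered to be a single hypoglycemic event". SAP 5.13.2.1 says "all consecutive hypoglycemic events in the same category, occurring within a 1-hour period may be considered to be a single hypoglycemic event".

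The SAP revision history (item 6) presents the edit to this section as added clarity. Protocol 10.3.1 and SAP 5.2 both say that a change to the protocol's methods, with its justification, belongs in the SAP or the clinical study report.

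**The concern.** The protocol names a specific hypoglycemia comparison, and the SAP section that should implement it analyzes something else. The protocol's rationale (Synopsis and 3.1) cites hypoglycemia as a drawback of glargine, so readers will look closely at this contrast. Glargine is typically given before bedtime (protocol 7.2.1.2), which makes the nocturnal comparison relevant. The trial is open-label, so a choice among event definitions left until after the data are available would be hard to defend.

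The merge rule matters for the rate. Suppose an asymptomatic 65 mg/dL is followed 20 minutes later by a symptomatic 52 mg/dL. The protocol's rule allows this to be one event. If the SAP's category is a row of its table, the two readings lie in different rows and both enter the ≤70 mg/dL count.

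**Working it through.** The documents give no hypoglycemia rate, power or sample size, so there is no planned figure to reproduce. The main check is a comparison of texts.

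**1. Side by side**

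| Item | Protocol 9.2.2.1 and 10.3.4.1 | SAP 5.13.2.1 |
|---|---|---|
| Documented symptomatic events | compared | defined, no analysis named |
| Severe events, total | compared | compared |
| Nocturnal events | compared | defined, no analysis named |
| All events ≤70 or <54 mg/dL, any symptom status | not named in 10.3.4.1 | compared |
| Merging within 1 hour | all consecutive values ≤70 mg/dL | events in the same category |
| Force of the merge rule | permissive | permissive |

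**2. Rest of the SAP.** SAP 5.12.4 uses documented symptomatic events in four composite responder endpoints. Each also requires an HbA1c target and no weight gain, so a patient can fail for any of three reasons and the hypoglycemia contrast cannot be read off. SAP 5.13.3 summarizes severe and level 2 events in the renal subpopulation. The sulfonylurea split in 5.13.2.1 is a summary of hypoglycemic events in general. None of these is a symptomatic or nocturnal comparison.

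**3. Merge rule.** Take two consecutive readings ≤70 mg/dL less than an hour apart. Each has one of 3 symptom states and one of 2 levels (<54, or 54 to 70), so there are 6 types and 6 × 6 = 36 ordered pairs. With merging applied, the protocol's rule gives one event for all 36. Under the SAP:

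- Category is symptom status by level: 6 pairs match, so 36 − 6 = 30 count as two events.
- Category is symptom status only (the ≤70 rows include values <54): 3 × 2 × 2 = 12 match, so 36 − 12 = 24 count as two.
- Category is the analyzed cut-off: in the ≤70 analysis all 36 match, so none count as two.

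These are possible pair types, not frequencies. A patient with any event counts once in the logistic model, so only the negative binomial rate can change.

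**4. What would be needed to bias the contrast.** All inputs here are assumptions, and the true glargine:tirzepatide rate ratio is set to 1.00.

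- Double counting, with d the share of extra events in an arm: ratio = (1 + d_glargine)/(1 + d_tirzepatide). Equal d gives 1.00. With 10% and 5%, 1.10/1.05 = 1.05. With 20% and 0%, 1.20. With 0% and 20%, 1/1.20 = 0.83.
- Unequal testing, with a the share of counted events found only by testing and k the testing-frequency ratio: ratio = (1 − a) + a·k. With k = 1, 1.00. With k = 1.25, 1.06, 1.13 and 1.19 for a = 25%, 50% and 75%. With k = 1.5, 1.13, 1.25 and 1.38.

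The documents supply no value for d, a or k. Required testing is the same for everyone: "Patients will be required to collect a daily BG and a weekly 4-point SMBG" (note to the Schedule of Activities). The difference between arms is that glargine doses are adjusted "based on the median value of the last 3 self-monitored fasting blood glucose (SMBG) values" (protocol 7.2.1.2).

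**The case against.** The strongest defense is that the SAP thresholds follow the protocol's own levels. Protocol 9.2.2.1 calls values <54 mg/dL clinically significant whether or not there are symptoms, and the stated objective is the occurrence of hypoglycemic events with no symptom limit. Method changes may be made in the SAP, and the revision history discloses that this section was edited. Severe hypoglycemia stays in the analysis, every symptom category is still defined, and SAP 5.2 allows additional analyses. A symptomatic endpoint is not free of bias either: it still needs a glucose test, and symptom reporting can depend on knowing that one takes insulin.

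Much of this stands. The threshold analyses are legitimate and should stay, and the documents do not establish that symptomatic events are the less biased choice. It does not explain why the protocol's named comparisons are missing, though. Permission to run extra analyses does not prespecify them, and calling the edit clarity gives no reason for the omission. A justification in the clinical study report would come after the data are known.

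On merging, it is fair that category is never tied to a row or a cut-off, and that neither rule is binding. But the SAP introduces its table as defining categories, so the row reading is the natural one. Wording that can change the count should be settled before analysis.

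**Conclusion.** The mismatch is established by the texts and needs no assumption. The symptomatic comparison and all nocturnal comparisons in protocol 10.3.4.1 have no counterpart in SAP 5.13.2.1, and no reason is stated. The narrower merge rule is also established. Its effect depends on what category means: 24 or 30 of 36 pair types under a row reading, none under a cut-off reading. It reaches only the episode rate.

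A reader might infer that the SAP's approach inflates the glargine rate through heavier testing and double counting, and so flatters tirzepatide. The documents do not support that. Required testing is equal across arms. Readings also guide decisions outside glargine titration: rescue criteria use the 4-point profile in all arms (9.2.2.2), and oral-drug reduction after hypoglycemia is not limited to one arm (7.4.2). Open-label use and titration on fasting values make extra testing under glargine plausible, but nothing shows it. Double counting leaves the rate ratio at 1.00 when it is equal in both arms and can move it either way when it is not. The ratios above 1 in the working illustrate assumptions; they do not estimate this trial.

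This should be corrected. It concerns a safety outcome outside type 1 error control and does not touch the primary or key secondary conclusions.

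**What to change.** In SAP 5.13.2.1, alongside the threshold analyses, apply the stated logistic and negative binomial models to documented symptomatic hypoglycemia (≤70 and <54 mg/dL) and to severe hypoglycemia, each total and nocturnal. If any of these is left out on purpose, state why.

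For counting, restore the protocol's rule and make it mandatory: all consecutive values ≤70 mg/dL within 1 hour are one event, assigned to the most serious category reached. Say how the event is classified when the symptoms and the lowest value come from different readings.

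The cost is SAP wording and a few extra tables. Symptom and nocturnal status are already in the event definitions; I assume they are recorded for each episode, since the case report form is not among the documents. The downside is sparser events in the symptomatic and nocturnal comparisons, where some models may have to give way to counts. If the glucose readings are in the database, a table of the number of readings per patient by arm would let readers judge the testing question directly.
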